3.2 BLRM (-Copula) Dose Escalation Recommendation Rules and Tools

Recommendations for the next dose level will be provided by BLRM (-Copula) models (considering available DLT information) together with the following dose escalation rules for BMS-986156 alone and in combination with nivolumab:

- Dose levels for the next cohort will be based on evaluating 4 potential recommendations: escalate, de-escalate, stay at same dose level, or stop and select a new dose other than pre-specified doses.
- Escalation by more than 1 dose level (dose skipping) is not permitted in real trial conduction.
- Based on model suggestions and a review of the available safety, PK, and PD data in combination with clinical recommendation, lower doses of BMS-986156 may be tested if none of the planned doses are found to be tolerated as monotherapy or in combination with nivolumab. Such decisions will be made after discussion and agreement between the investigators and the BMS Medical Monitor.
- No intra-subject dose escalation of BMS-986156 is allowed at any dose level.
- Dose de-escalation can be recommended by the model, and the final decision will be made based on clinical recommendation.

BLRM Stopping Rules during Dose Escalation

- If all of the current pre-specified doses are considered intolerable according to the pre-specified cutoff, then the model will recommend stopping the current dose level and a new dose level lower than the current lowest dose level will need to be identified (EWOC stopping).
- The maximum number of subjects in a dose level will be 12. This limit is set to avoid instances in which the model could recommend adding subjects indefinitely to a specific dose level due to uncertainty in the tolerability profile.
- If, for a specific dose level, 6 subjects have been treated and the chance of determining that dose level to be the “target” dose is $> 50\%$, then the model will suggest to stop the arm and declare the current dose level to be MTD.

4 INTERIM MONITORING CASE STUDY TO ILLUSTRATE BLRM (-COPULA) PROVISION OF RECOMMENDATIONS DURING DOSE ESCALATION

In order to provide a comprehensive view of the dynamics of the models, different hypothetical scenarios exploring all possibilities are examined. For the simplicity of illustration purposes, a static cohort size of 3 subjects is applied for dose levels 10 mg, 30 mg, 100 mg and 240 mg in the BMS-986156 monotherapy and for the dose level 30 mg in the combination setting. This cohort size could vary during the actual clinical trial, and the BLRM (-Copula) models are designed to fit various different cohort sizes, adaptively. In general, there are 4 possible scenarios for a specific dose level, which are 0 DLT observed in 3 total subjects in that cohort (denoted as 0/3), 1 DLT observed in 3 subjects (1/3), 2 DLTs observed in 3 subjects (2/3), and 3 DLTs observed in 3 subjects (3/3).

[figure not shown]
During interim monitoring, posterior probabilities will be updated when there is new DLT information available. The following three visualization plots will be produced to reflect the real time dose-DLT relationship, to quantify benefit (in the form of target dosing) and risk (in the form

of overdosing and underdosing) during model’s recommendation process, and to facilitate clinical team’s interpretation of the model recommendations for the final decision making:

- Dose-DLT profile for the doses ranging between 0 mg and 1000 mg (Figure 1).
- Stacking histograms displaying predictive probabilities on DLT rates classified into 3 different categories (Underdosing, Target dosing and Overdosing) (Figure 2).
- Box plots summarizing the Markov Chain Monte Carlo (MCMC) samples of predicted DLT rates for the 5 pre-specified dose levels (Figure 3).

Figure 1: Updated dose-DLT profile after incorporating prior information and all previous DLT information up to 30 mg (including all monotherapy DLT data for BMS-986156 up to 100 mg)

Interpretation and usage of Figure 1:

Figure 1 is a snapshot of an updated dose-DLT profile with DLT information available at dose level 30 mg for combination studies. The dose-DLT profile is captured with a continuous dose spectrum ranging from 0 mg to 1000 mg, which is a slice of the dose-DLT surface of the combination of two drugs with Nivolumab fixed at 240mg. For each dose within the range, there is a corresponding distribution of the predicted DLT rates calculated from the posterior samples of the model parameters. This figure will be updated each time new DLT information becomes available from the combination studies. Similar graphs will also be produced for the BMS-986156 monotherapy.

[figure not shown]
In Figure 1, there are 3 different quantiles (2.5%, 50%, and 97.5%) plotted to characterize the current trend of the toxicity profile (as shown by the 50% quantile), as well as the variation of the dose-DLT profile (as shown by the 2.5% percentile and the 97.5% percentile), according to the accumulation of DLT data from all previous and current dose levels. The toxicity boundaries (0.16 and 0.33) are illustrated in two dotted horizontal lines to benchmark the way in which the dose-DLT profile is trending.

Intermediate dose levels can be identified using different boundary cutoffs. For example, using the 50% percentile curve (green highlight), which represents the nearly average DLT distribution for each dose level, the 50 mg could be a potential intermediate dose level corresponding to the lower

pre-specified DLT rate boundary of 0.16, and the 375 mg could be a fitted MTD dose level associated with the upper boundary of 0.33.

Moreover, if all of the current pre-specified doses are considered intolerable (overdosing probabilities > 0.35 for combination therapy, a case not shown on the current Figure 1), the model will recommend to stop the current dose level, and the clinical team can leverage the current updated dose-DLT curve to pinpoint a new dose, which is lower than pre-specified lowest dose (10 mg) by using the DLT rate boundaries.

Figure 2: Updated stacking histogram after incorporating prior information and all previous DLT information up to 30 mg (including all monotherapy DLT data up to 100 mg for BMS-986156) to classify predicted DLT rates into 3 categories (Underdosing, Target Dosing and Overdosing)

Interpretation and usage of Figure 2:

Figure 2 is a snapshot of stacking histogram with DLT information available at dose level 30 mg for the combination studies. This figure will be updated each time new DLT information becomes available in the combination setting. Similar graphs will also be produced for the BMS-986156 monotherapy.

[figure not shown]
When recommending the next dose level, the model will first exclude doses that are intolerable (with overdosing probabilities > 35%, the rate that has been specified for BMS-986156 in combination with nivolumab). Among those qualified candidate doses that are considered “tolerable”, the model will select the dose that maximizes the probability of being within the target toxicity range (DLT rate of 16% up to 33%).

As illustrated in Figure 2, when there is 1 DLT observed out of 3 subjects for the dose level 30 mg, the distribution of predicted DLT rates will be characterized into possibilities falling into 3 different categories. First, dose levels of 240 mg and 800 mg for BMS-986156 are excluded according to the higher-than-cutoff (0.35 for combination therapy) overdosing probabilities (0.384 for 240mg and 0.595 for 800mg). Among the remainder of tolerable dose levels (10 mg, 30 mg, and 100 mg), the BLRM-Copula model recommends the dose that maximizes the probability of being within the target dosing interval. Therefore, the model’s recommendation would be to

escalate to 100 mg, which is associated with the highest target dosing probability of 0.311 compared with that of 30 mg (0.295) and 10 mg (0.263).

Similarly (although not shown on Figure 2), according to the rules specified above, the model could possibly recommend to de-escalate to a lower dose level than current treated dose level, extend the current dose level, or even recommend to stop and identify a new dose level lower than 10mg, the lowest pre-specified dose level. Please refer to description of Figure 1 for details on how to specify the new dose levels.

Figure 3: Updated box plot after incorporating prior information and all previous DLT information up to 30 mg in combination setting (including all monotherapy DLT data up to 100 mg for BMS-986156) for pre-specified dose levels

Interpretation and usage of Figure 3:

Figure 3 is a snapshot with DLT information available at dose level 30 mg for the combination setting. The dose-DLT distributions calculated from the posterior samples of the model parameters are characterized in the format of boxplots for the pre-specified dose levels. This figure will be updated each time there is new DLT information available. Similar graphs will also be produced for the BMS-986156 monotherapy.

This plot supplements the information provided in Figure 1. It allows for a more in-depth and focused visualization of general trend of dose-DLT relationship, as well as the magnitude and variability in the DLT rates for each pre-specified dose level.

4.1 Illustration for BMS-986156 Monotherapy Dose Escalation under Different Scenarios using the BLRM Model

[figure not shown]
According to safety consideration and clinical judgement, the dose level 10 mg is recommended as the starting dose for BMS-986156 monotherapy. With the current BMS-986156 prior specified in the Section 1.2.1 (Table 2) and all available DLT information up to 100 mg, a corresponding decision tree illustrating various models’ recommendations under all possible scenarios (for dose levels of 240 mg and 800 mg) is provided in Figure 4.

Tracing a branch of the decision tree in Figure 4 illustrates the decision making process. Taking the left-most branch of the tree as an example, starting at 10 mg, there was 0 DLT observed at

10 mg in the real clinical trial, the model recommended to escalate to 30 mg, one level above the current treated dose level according escalation rules per protocol (as detailed in Protocol Section 5.1). Additionally, there was 0 DLT observed at 30 mg in real data, the model recommended to escalate further one dose level to 100 mg. A further 0 DLT observation at 100 mg enabled the model to make a recommendation to escalate to 240 mg, currently 240 mg is within DLT observation period to collect DLT information.

As illustrated in Figure 4, there are 10 potential decision paths for dose levels 240 mg and moving onwards up to 800 mg, as real time clinical data has been taken into consideration of this decision tree. During the actual clinical study, the tree would be narrowed or deepened based on actual DLT. The clinical team will be able to leverage this decision tree to preview decisions at each interim monitoring step and to plan proactively.

APPENDIX 2 ECOG PERFORMANCE STATUS

ECOG PERFORMANCE STATUS^a	
0	Fully active, able to carry on all pre-disease performance without restriction
1	Restricted in physically strenuous activity but ambulatory and able to carry out work of a light or sedentary nature, eg, light house work, office work
2	Ambulatory and capable of all selfcare but unable to carry out any work activities. Up and about more than 50% of waking hours
3	Capable of only limited selfcare, confined to bed or chair more than 50% of waking hours
4	Completely disabled. Cannot carry on any selfcare. Totally confined to bed or chair
5	Dead

^a Oken MM, Creech RH, Tormey DC, Horton J, Davis TE, McFadden ET, and Carbone PP. Toxicity and Response Criteria of the Eastern Cooperative Oncology Group. Am J Clin Oncol 1982; 5: 649-655.

APPENDIX 3 RECIST 1.1

1 ASSESSMENT OF OVERALL TUMOR BURDEN AND MEASURABLE DISEASE

To assess objective response or future progression, it is necessary to estimate the *overall tumor burden at baseline* and use this as a comparator for subsequent measurements. Measurable disease is defined by the presence of at least one measurable tumor lesion. When CT scans have slice thickness greater than 5 mm, the minimum size for a measurable lesion should be twice the slice thickness.

Central assessments may be planned for this study. Copies of all scans should be kept at the site as part of the subject study file. At the Sponsor's discretion, scans may be collected centrally for further analysis.

At baseline, tumor lesions/lymph nodes will be categorized measurable or non-measurable as follows:

1.1 Measurable lesions

Measurable lesions must be accurately measured in at least one dimension (longest diameter in the plane of the measurement to be recorded) with a minimum size of:

- 10 mm by CT/MRI scan - (CT/MRI scan slice thickness no greater than 5 mm)
- 10 mm caliper measurement by clinical exam (lesions which cannot be accurately measured with calipers should be recorded as non-measurable)
- 20 mm by chest x-ray
- *Malignant lymph nodes*: To be considered pathologically enlarged *and* measurable, a lymph node must be ≥ 15 mm in *short* axis when assessed by CT scan (CT scan slice thickness recommended to be no greater than 5 mm). At baseline and in follow-up, only the *short* axis will be measured and followed.

1.2 Non-measurable lesions

- All other lesions, including small lesions (longest diameter < 10 mm or pathological lymph nodes with ≥ 10 to < 15 mm short axis), as well as truly non-measurable lesions.
- Lesions considered truly non-measurable include: leptomeningeal disease, ascites, pleural or pericardial effusion, inflammatory breast disease, lymphangitic involvement of skin or lung, abdominal masses/abdominal organomegaly identified by physical exam that in not measurable by reproducible imaging techniques.

1.3 Special considerations regarding lesion measurability

1.3.1 Bone lesions

- Bone scan, PET scan or plain films are *not* considered adequate imaging techniques to measure bone lesions. However, these techniques can be used to confirm the presence or disappearance of bone lesions.

- Lytic bone lesions or mixed lytic-blastic lesions, with *identifiable soft tissue components*, that can be evaluated by cross sectional imaging techniques such as CT or MRI can be considered as measurable lesions if the *soft tissue component* meets the definition of measurability described above.
- Blastic bone lesions are non-measurable.

1.3.2 Cystic lesions

- Lesions that meet the criteria for radiographically defined simple cysts should not be considered as malignant lesions (neither measurable nor non-measurable) since they are, by definition, simple cysts.
- ‘Cystic lesions’ thought to represent cystic metastases can be considered as measurable lesions, if they meet the definition of measurability described above. However, if non-cystic lesions are present in the same subject, these are preferred for selection as target lesions.

1.3.3 Lesions with prior local treatment

Tumor lesions situated in a previously irradiated area, or in an area subjected to other loco-regional therapy, are usually not considered measurable unless there has been demonstrated progression in the lesion.

1.4 Specifications by methods of measurements

1.4.1 Measurement of lesions

All measurements should be recorded in metric notation (mm). All baseline evaluations should be performed as close as possible to the treatment start and never more than 30 days before the beginning of the treatment.

1.4.2 Method of assessment

The **same method of assessment and the same technique should be used** to characterize each identified and reported lesion at baseline and during follow-up. Imaging based evaluation should always be done rather than clinical examination unless the lesion(s) being followed cannot be imaged but are assessable by clinical exam.

1.4.2.1 CT/MRI scan

CT/MRI is the best currently available and reproducible method to measure lesions selected for response assessment. Measurability of lesions on CT/MRI scan is based on the assumption that CT/MRI slice thickness is 5 mm or less. When CT scans have slice thickness greater than 5 mm, the minimum size for a measurable lesion should be twice the slice thickness.

1.4.2.2 Chest X-ray

Chest CT is preferred over chest X-ray, particularly when progression is an important endpoint, since CT is more sensitive than X-ray, particularly in identifying new lesions. However, lesions

on chest X-ray may be considered measurable if they are clearly defined and surrounded by aerated lung.

1.4.2.3 Clinical lesions

Clinical lesions will only be considered measurable when they are superficial and ≥ 10 mm diameter as assessed using calipers. For the case of skin lesions, documentation by color photography including a ruler to estimate the size of the lesion is suggested. As previously noted, when lesions can be evaluated by both clinical exam and imaging, imaging evaluation should be undertaken since it is more objective and may also be reviewed at the end of the study.

1.4.2.4 Ultrasound

Ultrasound is *not* useful in assessment of lesion size and should not be used as a method of measurement. If new lesions are identified by ultrasound in the course of the study, confirmation by CT or MRI is advised.

1.4.2.5 Endoscopy, laparoscopy

The utilization of these techniques for objective tumor evaluation is *not* advised.

2 BASELINE DOCUMENTATION OF 'TARGET' AND 'NON-TARGET' LESIONS

2.1 Target lesions

When more than one measurable lesion is present at baseline all lesions up to **a maximum of five lesions total (and a maximum of two lesions per organ) representative of all involved organs should be identified as *target lesions*** and will be recorded and measured at baseline.

Target lesions should be selected on the basis of their **size** (lesions with the longest diameter), be representative of all involved organs, and should lend themselves to ***reproducible repeated measurements***.

A ***sum of the diameters*** (longest for non-nodal lesions, short axis for nodal lesions) for all target lesions will be calculated and reported as the ***baseline sum diameters***. If lymph nodes are to be included in the sum, then as noted below, only the ***short*** axis is added into the sum. The baseline sum diameters will be used as reference to further characterize any objective tumor regression in the measurable dimension of the disease.

2.1.1 Lymph nodes

Lymph nodes merit special mention since they are normal anatomical structures which may be visible by imaging even if not involved by tumor. Pathological nodes which are defined as measurable and may be identified as target lesions must meet the criterion of a **short axis of ≥ 15 mm by CT scan**. Only the ***short*** axis of these nodes will contribute to the baseline sum. Nodes that have a short axis < 10 mm are considered non-pathological and should not be recorded or followed.

2.2 Non-target lesions

All other lesions (or sites of disease) including pathological lymph nodes should be identified as *non-target lesions* and should also be recorded at baseline. Measurements are not required and these lesions should be followed as ‘**present**’, ‘**absent**’, or in rare cases ‘**unequivocal progression**’. In addition, it is possible to record multiple non-target lesions involving the same organ as a single item on the case record form (eg, ‘multiple enlarged pelvic lymph nodes’ or ‘multiple liver metastases’).

3 TUMOR RESPONSE EVALUATION

3.1 Evaluation of target lesions

Complete Response (CR): **Disappearance of all target lesions**. Any pathological lymph nodes (whether target or non-target) must have reduction in short axis to < 10 mm.

Partial Response (PR): At least a **30% decrease in the sum of diameters of target lesions**, taking as reference the baseline sum diameters.

Progressive Disease (PD): At least a **20% increase in the sum of diameters of target lesions, taking as reference the smallest sum on study** (this includes the baseline sum if that is the smallest on study). In addition to the relative increase of 20%, the sum must also demonstrate an **absolute increase of at least 5 mm**. (*Note*: the appearance of one or more new lesions is also considered progression).

Stable Disease (SD): Neither sufficient shrinkage to qualify for PR nor sufficient increase to qualify for PD, taking as reference the smallest sum diameters while on study.

3.1.1 Special notes on the assessment of target lesions

3.1.1.1 Lymph nodes

Lymph nodes merit special mention since they are normal anatomical structures which may be visible by imaging even if not involved by tumor. Pathological nodes which are defined as measurable and may be identified as target lesions must meet the criterion of a **short axis of ≥ 15 mm by CT scan**. Only the *short* axis of these nodes will contribute to the baseline sum. Nodes that have a short axis < 10 mm are considered non-pathological and should not be recorded or followed.

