3.1.1.2 Target lesions that become ‘too small to measure’

All lesions (nodal and non-nodal) recorded at baseline should have their actual measurements recorded at each subsequent evaluation, even when very small (eg, 2 mm). If the radiologist is able to provide an actual measurement, that should be recorded, even if it is below 5 mm.

However, when such a lesion becomes difficult to assign an exact measure to then:

- If it is the opinion of the radiologist that the lesion has likely disappeared, the measurement should be recorded as 0 mm.

- If the lesion is believed to be present and is faintly seen but too small to measure, a default value of 5 mm should be assigned (note: in case of a lymph node believed to be present and faintly seen but too small to measure, a default value of 5 mm should be assigned in this circumstance as well). This default value is derived from the 5 mm CT slice thickness (but should not be changed with varying CT slice thickness).

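### Appendix 3 gives two incompatible instructions for a target lymph node that shrinks below 10 mm, so one scan could be scored SD, PR or NE

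*Combined protocol and SAP*

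**What the plan says.** Appendix 3 section 2.1.1 sets the rule for choosing nodes at baseline. A node qualifies as a target at a "short axis of ≥ 15 mm by CT scan", and smaller nodes below 10 mm are ignored. Section 3.1.1.1 sits in the chapter on response evaluation, under the special notes on target lesions. It reproduces that paragraph word for word, ending with the statement that nodes under 10 mm short axis "are considered non-pathological and should not be recorded or followed".

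The next subsection, 3.1.1.2, reads: "All lesions (nodal and non-nodal) recorded at baseline should have their actual measurements recorded at each subsequent evaluation, even when very small". It adds: "If the radiologist is able to provide an actual measurement, that should be recorded, even if it is below 5 mm". It assigns 5 mm to a node that is faintly visible but too small to measure, and 0 mm only when the radiologist thinks the lesion has probably gone.

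Section 3.1 defines PR as at least a "30% decrease in the sum of diameters of target lesions" relative to baseline. PD is at least a "20% increase in the sum of diameters of target lesions, taking as reference the smallest sum on study", together with a rise of 5 mm or more. Protocol section 5.4 has the investigator assess response and refers to Appendix 3 for the criteria. Section 8.3.2.2 derives ORR, DOR and PFSR from those assessments.

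**The concern.** A target node measured at 9 mm on treatment cannot be both left unrecorded and recorded at its actual size. Because 3.1.1.1 stands in the response chapter, a site may take its last sentence as the on-treatment rule for target nodes. No text confines it to baseline selection or says which subsection prevails.

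Response is computed from the sum of target diameters, so whether the node is in the sum can change the category. Two sites reading different subsections could score identical scans differently. The secondary efficacy endpoints would then depend partly on which paragraph a site followed.

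**Working it through.** **Inputs.** The 15 mm node minimum and the PR and PD thresholds come from Appendix 3 sections 3.1 and 3.1.1.1. The lesion sizes below are illustrative assumptions, since the documents give none. None of the plan's stated figures depends on this point, so there is none to reproduce.

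**Step 1: what each section implies for a target node now at 9 mm.**

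| Appendix 3 section | Implication |
|---|---|
| 1.1 | Short axis is measured at baseline and during follow-up |
| 3.1 (CR) | The node must be shown to be under 10 mm, so it has to be measured |
| 3.1.1.1 | Read literally: not recorded, not followed |
| 3.1.1.2 | Actual measurement recorded |
| 4.1 | If only some lesions are measured: NE, unless it can be argued that the missing lesion would not alter the result |

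Three of these support continued measurement and one opposes it. The fifth says what happens when a measurement is missing.

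**Step 2: one scan, three scores.** Baseline: node 16 + lung 30 = 46 mm. Follow-up: node 9, lung 28.

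- Node measured: 9 + 28 = 37 mm; (37 - 46)/46 = -19.6%, SD.
- Node left out of the sum: 28 mm; (28 - 46)/46 = -39.1%, PR.
- Node unrecorded and section 4.1 applied: NE, subject to its exception.

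**Step 3: the next scan.** Node 10, lung 28.

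- Node measured throughout: 38 against a smallest sum of 37; +1 mm, 1/37 = +2.7%, not PD.
- Node left out, then put back: 38 against 28; +10 mm, 10/28 = +35.7%, PD.
- Node left out and kept out: 28 against 28; no change, not PD.

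**Step 4: how general this is.** Let N be the baseline node and T an unchanged non-nodal sum. Omitting the node gives a 30% fall when N/(N + T) >= 0.30, that is T <= (7/3)N.

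- For N = 15 the limit is T = 35 mm. With the node measured at 9 mm, the change there is (9 - 15)/50 = -12%.
- For N = 20 the limit is T = 46.7 mm, and the change is (9 - 20)/66.7 = -16.5%.

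A node returning at 10 mm to a sum T that excluded it meets the PD rule when 10/T >= 0.20, that is T <= 50 mm. Not every case changes category twice. Node 20 + lesion 60 = 80 mm, going to 9 + 56, is 65 mm (-18.8%, SD) measured and 56 mm (-30.0%, PR) omitted. Return of the node at 10 mm then gives 66 against 56, +17.9%, which is not PD.

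**Step 5: direction.** Node 30 + lesion 40 = 70 mm, going to 9 + 40 = 49 mm, is -30.0%: a PR when the node is measured. Scored NE, that scan contributes no response. Omission can therefore add a PR (step 2) or remove one. In a 40-subject cohort each changed subject moves ORR by 1/40 = 2.5 points.

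**Step 6: safeguards.** Confirmation at least 4 weeks later (Appendix 3, 4.1.1) does not help if the node is omitted at both scans. Central reading is only a possibility (Appendix 3, section 1). For analysis, protocol section 3.11.1.1 dates progression at the initial event even when treatment continues.

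**The case against.** The strongest reply is that 3.1.1.1 is not a follow-up rule at all. Its content is about which nodes qualify as targets and what enters the baseline sum, and it never mentions a node that has shrunk. The text that does address follow-up (1.1, the CR definition and 3.1.1.2 with its default for nodes) consistently requires measurement. This is largely right and makes duplicated baseline text the likely explanation. The sentence still stands, unqualified, in the section on assessing target lesions.

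A reader might go further and infer that the plan produces false PRs and false PDs, inflates ORR, or takes subjects off treatment. The documents do not support that:

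- Section 3.1.1.1 does not say to enter 0 mm, and 3.1.1.2 reserves that value for a lesion that has probably disappeared. Under 4.1 an unrecorded target node would generally make the time point NE.
- The PD result requires a node that was not to be followed to be followed after all and returned to the sum.
- Protocol sections 3.1 and 3.11 tie discontinuation for progression to confirmed progression, and 3.11.1 allows qualifying subjects to continue beyond initial PD.
- Nothing shows that any site used the literal reading.

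The endpoints are also secondary, no hypothesis is formally tested (section 1.3), and continuation decisions rest on the totality of data (sections 3.7 and 8.1.2). That limits the stakes but does not justify leaving two opposite instructions in place.

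**Conclusion.** The contradiction is real and should be corrected. For a shrunken target node, the same scan could be SD, PR or NE according to the subsection applied, and a node put back into the sum could make a 1 mm change read as PD. The arithmetic is exact for the illustrative sizes and follows from the protocol's own thresholds.

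The direction and size of the effect on ORR, DOR and PFSR cannot be determined. The documents give neither the frequency of target nodes, nor measurement error, nor how sites read 3.1.1.1. Any simulated rate would rest wholly on assumed values, so none is offered. The conclusion is that the scoring rule is ambiguous, not that the results are biased in a known direction.

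**What to change.** Keep the instruction not to record or follow nodes under 10 mm only in Appendix 3 section 2.1.1, for baseline selection. In 3.1.1.1, replace it with the rule already in 3.1.1.2: the actual short axis of every node chosen as a target at baseline is recorded and added to the sum at each assessment, including below 10 mm. State that the sum therefore need not be zero at CR. Derive ORR, DOR and PFSR on that sum.

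The cost is one sentence and a clarification to sites. No additional scans are needed. Appendix 3 section 1 has sites keep copies of all scans, so any omitted node can be remeasured. A few response categories may change if any site did leave nodes out.
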